- For clarity and consistency, the exclusion criteria, switch exclusion criteria, and the stopping rule concerning hepatic decompensation have been updated.
- The normal range of hemoglobin varies with age in pediatric patients; therefore the exclusion criterion and switch exclusion criterion for hemoglobin have been amended to below the lower limit of normal (<LLN) as opposed to using fixed cut-off values of <11 g/dL for females and <12 g/dL for males. This may prevent unnecessary exclusion of some eligible patients.
- The renal exclusion criterion has been amended to exclude patients with evidence of renal impairment.
- Serum alanine aminotransferase (ALT) >10 × upper limit of normal (ULN) at switch baseline has been added into the switch exclusion criteria as treatment of Pegylated-Interferon Alfa-2a should normally not be initiated if ALT is >10 × ULN.
- Changes have been made to the stopping rules to align with the current approved prescribing information, including removal of certain stopping rules, and separation of stopping rules into those where treatment must be discontinued and those where treatment discontinuation should be considered.
- Scheuer Scoring system has been added in Appendix 1 (Liver Biopsy Scores) to help sites using this scoring system to classify the degree of liver fibrosis.

Additional changes to the protocol are as follows:

- The Medical Monitors' details have been updated.
- For clarity and consistency of occurrences of "post-treatment" have been changed to "post-end of treatment"
- Additional rationale for the untreated control arm has been included, including procedures for minimizing the risk of bias in this open-label study.
- Given the different schedule of assessments for the treatment group compared with the untreated group, it is practically not possible to blind the assessor within this

study. Therefore, the blinding of central laboratory to the treatment assignment has been removed.

- Additional clarity has been included regarding administration of the Children's Depression Inventory and assessment of patients with symptoms of major depression.
- Additional clarity regarding the timepoint and contents of the primary safety analysis has been added. In addition, following safety outcome measures until 1, 2, 3, 4, and 5 years post-end of treatment have been added.

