8.2.5.3 Safety Data Analysis

The primary safety analysis will compare safety in Group A with Group B *at 24 weeks post-end of treatment/end of untreated observation*. The safety data of Group A and Group B will be qualitatively evaluated alongside subjects in Group C and the switch arm.

- *Incidence, nature, and severity of serious and non-serious AEs (including neurological and psychiatric events)*
- *Reasons for the discontinuation of any study medication*
- *Dose modifications for laboratory abnormalities and clinical AEs*
- *Changes in vital signs and laboratory tests from screening/baseline, including thyroid function*
- *Effect on growth (height and weight)*

The following safety outcome measures will be assessed using descriptive statistics at 1, 2, 3, 4, and 5 years post-end of treatment:

- *Incidence, nature, and severity of persisting AEs, new-onset related SAEs/ non-serious AEs of special interest*
- *Changes in thyroid function from screening/baseline*
- *Effect on growth (height and weight)*

AEs: AEs will be assigned preferred terms and categorized into body systems according to the Medical Dictionary for Regulatory Activities (MedDRA) classification of the World Health Organization (WHO) terminology. Descriptive statistics will be used to summarize safety parameters by group. Neurological and psychiatric AEs will be assessed in further detail, including persistence and duration, as well as new onset of SAEs and non-serious AEs of special interest related to PEG-IFN reported during the extended long-term follow-up period of this study.

Laboratory Safety Data: The laboratory data (including thyroid function) will be analyzed according to Roche's "International Guideline for the Handling and Reporting of Laboratory Data".

Growth (weight and height): The continuous growth will be analyzed with Residual Maximum Likelihood, or analysis of covariance. The assumptions of the analysis such as normally distributed residuals will be assessed. If necessary, rectifying transformations shall be applied. Growth (height) velocity will be explored.

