4.6.3 Laboratory Data

If more than one visit occurred during a single visit window, then the laboratory data closest to the scheduled visit day will be used. If the two laboratory assessments were equidistant from the scheduled visit day then the later assessment will be used; if there was more than one 'later assessment', that is recorded on the same date and time, then the 'worst' case will be used. The exception is the data within the Baseline visit; in this case, if two or more samples were collected on the day that was closest to the Baseline

⁵ The Division of AIDS (DAIDS) Table for Grading the Severity of Adult and Pediatric Adverse Events should be used to assist in the assessment of intensity

target day, then the earliest sample was selected; if the sample collection time was the same then the worst value was selected.

Laboratory data not reported in International System of Units (SI units) will be converted to SI units before further processing. The reference ranges of each investigator/local laboratory will be used for all parameters.

Listings of laboratory parameters at each visit will be provided by treatment group for Safety population. Summary tables of mean change from baseline of laboratory parameters will be provided (some laboratory parameters will be summarised as multiples of ULN instead of raw values: ALT, AST, alkaline phosphatase (ALP), total bilirubin, gamma glutamyl transpeptidase (GGT)).

Lowest and/or highest values of laboratory data post-baseline will be summarized by treatment group using the DAIDS grading system (except for those laboratory parameters with project-specific grandings provided in [Figure 2](#)). Shift table of the lowest and/or highest post-baseline DAIDS grade for laboratory parameters will be provided (except for those laboratory parameters with project-specific grandings provided). Patients with one or more thyroid function values outside the normal range and with change from baseline meeting pre-specified cutoffs (for free triiodothyronine [FT3] and free thyroxin [FT4], it is increase $\geq 20\%$ or decrease $\geq 20\%$; for thyroid-stimulating hormone [TSH], it is increase $\geq 30\%$) will be summarized and listed by treatment group in Safety Population.

Figure 2 Potentially Clinically Relevant Laboratory Abnormalities for Neutrophil, Lymphocyte, Platelet Counts, Hemoglobin, Triglyceride Concentration and ALT

Parameter	Project Specific	Normal				

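### SAP 4.6.3 plans no baseline shift table for the six Figure 2 laboratory parameters, ALT above all, and separately counts no hemoglobin value between 10.0 g/dL and LLN

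*SAP*

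**What the plan says.** SAP 4.6.3 has two adjacent sentences on laboratory grades. The first: "Lowest and/or highest values of laboratory data post-baseline will be summarized by treatment group using the DAIDS grading system", with an exception that points to Figure 2. The second promises a shift table of the lowest or highest "post-baseline DAIDS grade for laboratory parameters will be provided (except for those laboratory parameters with project-specific grandings provided". Figure 2 is titled "Potentially Clinically Relevant Laboratory Abnormalities for Neutrophil, Lymphocyte, Platelet Counts, Hemoglobin, Triglyceride Concentration and ALT", so those six parameters leave both DAIDS outputs. The first exception points to Figure 2 as the substitute; the second names none. No other part of the SAP specifies a shift table on the Figure 2 bands.

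Two outputs that refer to baseline, or allow it to be read off, stay for all parameters: "Summary tables of mean change from baseline of laboratory parameters will be provided" and "Listings of laboratory parameters at each visit will be provided by treatment group for Safety population". SAP 4.6.3 adds a summary of ALT flares (above 10×ULN, and between 5 and 10×ULN) and summaries of ALT and neutropenia by age group. SAP 4.6.2 reports laboratory abnormalities leading to dose modification or withdrawal.

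Protocol 8.2.5.3 includes in the primary safety analysis "Changes in vital signs and laboratory tests from screening/baseline, including thyroid function". On hemoglobin, the rationale at the front of Protocol Version E says "The normal range of hemoglobin varies with age in pediatric patients" and replaces fixed cut-offs with LLN. LLN is now the limit in Protocol 4.3 and 4.8.2 and in per-protocol exclusion 7 (SAP 4.1.2).

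**The concern.** A table of worst post-baseline values says little about treatment if children can already be in an abnormal band at entry and no baseline category is crossed with it. The safety comparison is one of the trial's aims. Protocol 3.1.2.2 reports a high incidence of neutropenia in treated children, and ALT flares get their own summary. The SAP does count children by change from baseline elsewhere: thyroid values (SAP 4.6.3) and growth percentile drops of 15% or more (SAP 4.6.5.2). For these six parameters it does not.

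The hemoglobin point is separate. The protocol gave up fixed limits for eligibility because normal varies with age. Figure 2 then applies one fixed limit to children aged 3 to under 18.

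**Working it through.** The plan states no figure to reproduce, so the first check sets entry limits (Protocol 4.2 and 4.3) against the Figure 2 bands. The header row of Figure 2 is broken in the text available. I read its first value column as normal and take the Figure 2 bands to replace DAIDS grades in the worst-value summary; both are inferences.

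| Parameter | Entry limit | First band beyond the normal column | Eligible entry values already beyond it |
|---|---|---|---|
| ALT | >ULN to ≤10×ULN | 1.25–2.5×ULN | 1.25 to 10×ULN (three bands) |
| Neutrophils, ×10⁹/L | not <1.5 | 1.5 to <2.0 | 1.5 to <2.0 only |
| Platelets, ×10⁹/L | not <90 | 75 to <100 | 90 to <100 only |
| Lymphocytes, ×10⁹/L | none | 1.0 to <1.5 | any |
| Triglycerides, mmol/L | none | 1.13 to <2.26 | any |
| Hemoglobin, g/dL | not <LLN | 8.5 to <10.0 | none if LLN ≥10.0 |

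**ALT.** Take one child who enters at 6×ULN and peaks at 6×ULN, and another who enters at 1.5×ULN and peaks at 6×ULN. The changes are 0 and 4.5×ULN. Both fall in the >5.0–10×ULN band and both count as a 5–10×ULN flare. Baseline ALT is tabulated in SAP 4.3.1, but with cuts at 1, 2, 5 and 10×ULN against 1.25, 2.5, 5 and 10×ULN in Figure 2, and it is not crossed with later values.

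**Neutrophils.** A fall from 1.8 to 1.6 is (1.8 − 1.6)/1.8 = 11%; from 5.0 to 1.6 it is (5.0 − 1.6)/5.0 = 68%. Both land in 1.5 to <2.0. With 145 children split 2:1 (97 and 48), and assuming 5–20% enter in that band:
- Group A: 97 × 0.05 = 4.9 to 97 × 0.20 = 19.4, about 5 to 19 children.
- Group B: 48 × 0.05 = 2.4 to 48 × 0.20 = 9.6, about 2 to 10 children.

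A simulation gives a range. Assumptions, none from the documents: lognormal counts, median 2.8–4.0, between-child CV 30–40%, within-child CV 20–30%, screening value ≥1.5.
- About 2–19% of children are below 2.0 at baseline.
- With no drug effect and 5 draws, 17–42% of those tabulated below 2.0 were already there at baseline.
- With 13 draws and an assumed 40% fall, that share is 4–21%.

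**Number of draws.** Post-baseline hematology is scheduled 14 times in Group A by Protocol Table 2 (13 by SAP Appendix 2 Table 1) and 5 times in Group B. Under the same assumptions with no drug effect, any value below 2.0 occurs in 7–47% of children with 5 draws and 12–65% with 13.

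**Hemoglobin.** The documents give no LLN. For an assumed LLN of 10.5 to 13 g/dL, a fall from LLN to 10.0 is 0.5/10.5 = 5% up to 3.0/13 = 23%, and both ends stay in the ≥10.0 band. Simulation, again on assumptions (mean 13.0, SD 0.9, within-child SD 0.4, LLN 11–12, true fall 1 g/dL):
- 5 draws: 27–63% of children have a value below LLN, 0.5–3.5% below 10.0.
- 13 draws: about 35–72% and 1–6%.

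**The case against.** The strongest reply is that the second exception only removes these parameters from a shift of DAIDS grade and may be meant, like the first, to move them to Figure 2. Table layouts are in DAP Module 2, and the protocol refers laboratory analysis to a sponsor guideline; neither is among the documents. This stands in part. A shift table might exist in Module 2, and a reader should not infer that none exists anywhere. But SAP Section 1 makes the SAP the place for methods and gives Module 2 the layouts, and the SAP as written excludes the table without naming a substitute.

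Four stronger readings are tempting and are not supported:
- That the missing shift table hides hemoglobin falls. It does not; the 10.0 g/dL cut-off does. A fall from 13.5 to 10.2 would show no shift on the Figure 2 bands either.
- That entry values contaminate the bands behind the dose rules. Protocol 6.2.5.1 and 6.2.5.2 act at neutrophils below 0.75 and platelets below 50, while entry limits are 1.5 and 90. If screening values hold to baseline, only the mildest band is affected.
- That toxicity is understated for the counts. Entry values balance in expectation under randomization, and Group A's extra draws can push its worst-value counts up.
- That only a mean change is left. Listings and abnormalities leading to dose modification or withdrawal remain, as does the special-interest event of ALT or AST above 3× baseline with raised bilirubin or jaundice.

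It is also fair that Figure 2 is labelled as potentially clinically relevant abnormalities, so a hemoglobin threshold below LLN may be deliberate, and that Protocol 8.2.5.3 asks for changes without requiring categorical shifts.

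**Conclusion.** The concern holds in a limited form. As written, SAP 4.6.3 yields no categorical laboratory table that separates abnormalities present at entry from new ones for the six Figure 2 parameters. The gap is widest for ALT, where raised entry values are required and the upper stratum starts in the flare range (assuming screening values persist to baseline). It is confined to the mildest band for neutrophils and platelets, and it is open for lymphocytes and triglycerides.

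Separately, a hemoglobin fall from normal to between 10.0 g/dL and LLN is counted in no categorical laboratory table, since DAIDS grading is also switched off for it.

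The overlap of limits and bands follows from the documents. Every percentage of children rests on assumed distributions. Which way the group comparison of counts would be distorted is not established. The primary efficacy result, sample size and data collection are unaffected. This is a cheap improvement to safety reporting.

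**What to change.** In SAP 4.6.3:
1. Replace the shift-table exception with baseline-by-worst-post-baseline shift tables on the Figure 2 bands for all six parameters.
2. Report ALT flares by baseline ALT category (<5×ULN, ≥5×ULN), the split already used for stratification and in SAP 4.4.3.
3. Split the top hemoglobin band into ≥LLN of the testing laboratory and 10.0 g/dL to <LLN.

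Check DAP Module 2 first; if it already holds such tables, the SAP wording only needs to say so. The data are already collected. The cost is a few more tables and a less favourable anaemia count. The new tables still use worst values, so they do not remove the imbalance in draws (14 or 13 against 5); a footnote giving the scheduled number per group would make that visible.

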^a Parameter does not need to be repeated at re-screening if performed within 6 months prior to baseline, unless dictated by a change in the subject's medical condition or the parameter accounted for the original screen failure.

^b To be performed by local laboratory.

^c To be performed by a local laboratory in countries activated prior to April 2013, and by a central laboratory in countries activated after April 2013.

^d To be performed by central laboratory.

^e Estimated creatinine clearance will be calculated internally at baseline/switch baseline.

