5.4 LABORATORY ASSESSMENTS

Laboratory assessments post-screening are noted in [Table 6](#) and will be carried out as per the schedules in [Table 2](#) to [Table 4](#).

Table 6 Laboratory Assessments

Hematology ^a	Complete blood count (hemoglobin, hematocrit, total WBC count, differential WBC count [neutrophils, lymphocytes, monocytes, eosinophils, basophils]), platelet count], INR
Clinical chemistry ^a	ALT, AST, GGT, total bilirubin, alkaline phosphatase, total protein, albumin, BUN/urea, creatinine ^d , uric acid, total calcium, phosphorus, cholesterol, triglycerides, random glucose, sodium, chloride, potassium
Urinalysis ^b	Dipstick with subsequent microscopic evaluation if positive for blood.
HCG pregnancy test ^b	Urine or serum pregnancy test for females of childbearing potential at any time secondary amenorrhea of more than 1 week occurs. The result of the baseline pregnancy test must be available prior to randomization and commencement of treatment.
Thyroid function tests ^c	FT3, FT4, TSH, TPO antibodies ^e
Immunology ^c	ANA ^e
HBV serology and virology ^c	HBeAg, anti-HBe, HBsAg, anti-HBs, quantitative HBsAg and HBeAg, HBV-DNA

^a To be performed by a local laboratory in countries activated prior to April 2013, and by a central laboratory in countries activated after April 2013.

^b To be performed by local laboratory.

^c To be performed by central laboratory.

^d Estimated creatinine clearance will be calculated by the Sponsor at Week 24/SW 24.

^e PEG-IFN–treated subjects only.

Samples for central analysis will be sent to one or more central laboratories or to the Sponsor for analysis.

Where any analysis is performed by a local laboratory, normal ranges for the local laboratory parameters must be supplied to Roche or designee before the study starts and at any point that the normal ranges are changed.

The results from all hematology and clinical chemistry investigations should be available and reviewed by the investigator or his/her authorized designee before instructing the subject on whether PEG-IFN dosing should continue unchanged or be modified.

See Section 6.2.5 and 7.1.3.1 for follow-up of laboratory abnormalities.

All virological and serological efficacy parameters will be assessed by the central laboratory.

The total volume of blood loss for laboratory assessments (excluding PK and RCR) will be approximately as follows:

- Group A and Group C: 228 mL
- Group B non-switch: 158 mL
- Group B switch: up to 312 mL

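### The SAP's thyroid flag cannot count an isolated fall in TSH, and its local-range sentence conflicts with central laboratory testing

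*SAP*

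**What the plan says.** SAP 4.6.3 defines the thyroid summary as "Patients with one or more thyroid function values outside the normal range and with change from baseline meeting pre-specified cutoffs". For FT3 and FT4 the cut-off is a rise or a fall of at least 20%. For TSH the text is "for thyroid-stimulating hormone [TSH], it is increase", with a threshold of 30%, and nothing follows for a decrease.

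On reference ranges, the same section says: "The reference ranges of each investigator/local laboratory will be used for all parameters".

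The protocol places the thyroid tests elsewhere. In Table 5 (Section 5.1) the screening thyroid tests carry the footnote "To be performed by central laboratory". In Table 6 (Section 5.4) the row "FT3, FT4, TSH, TPO antibodies" has the same assignment after screening. Both tables also make hematology and chemistry central in countries activated after April 2013, and local in those activated before. Section 5.4 asks for local ranges only in one situation: "Where any analysis is performed by a local laboratory, normal ranges for the local laboratory parameters must be supplied".

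**The concern.** The protocol (8.2.5.3) includes change in thyroid function in the primary safety comparison and does not restrict it to one direction. The flag is the only thyroid-specific laboratory count of patients that the SAP defines. If one direction of TSH change cannot trigger it, the Group A versus Group B comparison in that table leaves out one kind of abnormality by construction.

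The flag also requires a value outside the normal range, so it depends on which range is used. Read literally, the SAP sets a centrally measured result against another laboratory's limits, or calls for limits that the protocol never asks sites to supply for that test.

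**Working it through.** **TSH direction.** The plan states no figure to reproduce, so the check is on the logic of the rule. The inputs from SAP 4.6.3 are: out of range, and change c = (value − baseline) / baseline, with |c| ≥ 20% for FT3 or FT4, or c ≥ +30% for TSH. The documents give no thyroid ranges. The ranges and values below are illustrative assumptions: TSH 0.5–4.5, FT4 10–22, FT3 3.5–6.5; baseline TSH 2.0, FT4 15, FT3 5. The last column adds a TSH fall of at least 30%, purely to test the effect.

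| Pattern (TSH / FT4 / FT3) | Changes | As written | With a decrease limb |
|---|---|---|---|
| Low TSH alone (0.05 / 17 / 5.5) | −97.5% / +13.3% / +10% | not counted | counted |
| Low TSH, high FT4 and FT3 (0.01 / 35 / 10) | −99.5% / +133% / +100% | counted | counted |
| High TSH alone (9 / 14 / 5) | +350% / −6.7% / 0% | counted | counted |
| High TSH, low FT4 and FT3 (30 / 6 / 3) | +1400% / −60% / −40% | counted | counted |

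Only the first pattern changes status. This does not depend on the assumed ranges: a fall gives c < 0, which can never reach +30%.

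**How many children.** The documents give no frequency for low TSH alone. Planned Group A is 2/3 × 145 ≈ 97. Under an assumed frequency of 1%, 0.01 × 97 ≈ 1; under 10%, 0.10 × 97 ≈ 10. These show scale only and are not estimates.

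**Reference range.** The passages side by side:

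| Tests | Laboratory (Protocol Tables 5 and 6) | Range-dependent output in SAP 4.6.3 |
|---|---|---|
| FT3, FT4, TSH | Central everywhere | The thyroid flag |
| Chemistry | Central in countries activated after April 2013 | ALT, AST, ALP, total bilirubin and GGT as multiples of ULN; ALT grading and flares |
| Hematology | Central in countries activated after April 2013 | Neutrophils, lymphocytes, platelets and hemoglobin use fixed cut-offs (SAP Figure 2), so no range enters their grading |
| Urinalysis, pregnancy test | Local everywhere | No conflict |

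Triglycerides are also graded on fixed cut-offs in Figure 2. No miscount can be computed, because the documents contain neither central nor local ranges.

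**The case against.** The strongest reply is that the gap is narrow and the data remain available. A low TSH with a qualifying FT3 or FT4 change is still counted. Every TSH value appears in the by-visit listings and contributes to the mean-change tables. An abnormal result that is serious, stops treatment or changes concomitant therapy is recorded as an adverse event under Protocol 7.1.3. The SAP also plans this: "Lowest and/or highest values of laboratory data post-baseline will be summarized by treatment group using the DAIDS grading system".

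Most of that stands, but it does not supply the missing count. Listings give no count by group, rises and falls can cancel in a mean, and adverse events capture only results with consequences. Whether the grading scale covers TSH cannot be checked from the documents.

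On ranges, the reply is that the sentence is probably loose wording. Local thyroid ranges are not called for when the test is central, SAP 4.4.2 takes the ULN for normal ALT from each laboratory, and the protocol's ALT eligibility criterion uses the testing laboratory's range. That is a plausible reading, though the SAP does not state it for these outputs.

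A reader might infer three stronger things that the documents do not support:

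- That thyroid abnormalities in general are miscounted. Only isolated TSH falls are shown to be missed.
- That all thyroid results, and all laboratory results in later-activated countries, are judged against the wrong range. Use of a wrong range is not shown, urinalysis and pregnancy tests are always local, and several parameters use no range in their grading.
- That the flag distorts the Year 1 to 5 thyroid outcome. SAP 4.1 assigns its analyses to the primary CSR unless otherwise specified, and Protocol 8.2.5.3 attaches no flag or direction to the long-term outcome.

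**Conclusion.** The point holds in two limited parts. First, followed as written, the flag can never count an isolated out-of-range fall in TSH. FT3 and FT4 are treated symmetrically, and no reason is given for treating TSH differently. The error is an undercount in one direction, in one descriptive safety summary. Its size cannot be derived from the documents; the figure of about 1 to 10 children rests wholly on the assumed 1% to 10% of about 97.

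Second, the local-range sentence contradicts the protocol's central testing. This is a wording conflict that affects the thyroid flag, the ULN-multiple summaries, and ALT grading and flares. It is not a demonstrated miscount. Neither part affects the primary endpoint, the significance level, the power or the sample size.

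**What to change.** In SAP 4.6.3:

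- Add a pre-specified TSH decrease criterion and report TSH rises and falls separately by group. The sponsor should choose the cut-off, since the documents supply none. Mirroring the existing rule would give a 30% fall; on a ratio scale the mirror of +30% is 1 − 1/1.30 ≈ 23%. If the increase-only rule is deliberate, state the reason.
- Replace the range sentence with one saying that the reference range of the laboratory that tested the sample is used. This also agrees with SAP 4.4.2.

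The cost is two SAP sentences and a small programming change before database lock. TSH is already collected, so no new data are needed.
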